A pilot randomized clinical trial of cognitive-behavioural therapy for insomnia in adolescents  
with persistent post-concussion symptoms

Date: September 19, 2018

Supplement 1.  
Trial Protocol.

Trial Design

This study involved a single-blind, parallel-group randomized control trial design comparing CBT-I and a treatment as usual (TAU) control group. Eligible participants were randomly assigned to either the active treatment (CBT-I) or the TAU control group using a gender blocked computer-based randomization tool (<https://www.randomizer.org/>). Participants who were randomized to the TAU condition were offered CBT-I after all follow-up measures were completed. Researchers administering the assessments were blinded to the randomization results. The trial followed and is reported according to CONSORT guidelines . The outcome measures chosen were informed by recommendations for assessing outcome in insomnia trials, including assessment of potential secondary gains associated with treatment . The study received was approved by the University of Calgary Conjoint Health Research Ethics Board (REB16-1166).

Participants and Procedures

Participants were recruited from the Alberta Children's Hospital (ACH) Brain Injury Clinic between October 2016 and August 2017. Adolescents were referred to the ACH Brain Injury Clinic based on persistent post-concussion symptoms. A total of 78 adolescents were approached, of whom 51 indicated interest in the study. Interested participants who could be contacted were screened for insomnia over the phone using the Insomnia Severity Index (ISI). If the potential participant received a score of  $\geq 12$  on the ISI, they were invited to attend a baseline session to determine eligibility. Of the participants who expressed interest in the study, 18 could not be reached for further screening and 9 did not meet the inclusion criteria. The final sample

consisted of 24 youth who were randomized to CBT-I (n=12) or TAU (n=12). Participant flow is presented in Figure 1.

Inclusion criteria included: (1) 12-18 years of age; (2) diagnosed with a concussion by a nurse practitioner or physician at the ACH Complex Concussion Clinic (i.e., concussion was defined as an traumatic injury to the head, at least one reported symptom [e.g., dizziness, headache, nausea] at the time of the injury, and a Glasgow Coma Scale rating of  $\geq 13/15$  at 30 minutes after injury, or loss of consciousness  $< 30$  minutes, or post-traumatic amnesia  $< 24$  hours); (3) being at least 1 month but no more than 12 months post-injury to ensure symptoms were no longer acute, yet current and persistent; (4) reporting elevated symptoms of insomnia measured by an Insomnia Severity Index score of  $\geq 12$ ; and (5) ability to attend in-person treatment sessions. Exclusion criteria included: 1) moderate or severe TBI (i.e., Glasgow Coma scale rating of  $\leq 12$ , loss of consciousness exceeding 30 minutes, and/or post-traumatic amnesia exceeding 24 hours); and 2) visual, hearing, motor, and/or language deficits that would hinder the completion of questionnaires or engagement in CBT-I.

Assessments took approximately 45 minutes to complete and were conducted at baseline, post-treatment, and follow-up at four weeks after treatment. Assessments and treatment took place at the University of Calgary. In the first assessment at baseline, informed consent from the parent and informed assent from the adolescent were obtained in addition to baseline questionnaire data. If deemed eligible, participants were asked to fill out online sleep diaries for seven days. After the sleep diary was completed, participants were randomized to either CBT-I or TAU groups. If randomized to the CBT-I group, a study therapist contacted the participant and scheduled the first session. Seven weeks later, the post-treatment assessment was completed via online questionnaire and sleep diary. A third assessment was completed approximately four

weeks after treatment (follow-up) via online questionnaire and sleep diary. A research coordinator who was blinded to group membership collected all data. After the third assessment was completed, participants in the TAU group were invited to take part in the six-week CBT-I treatment (additional outcome measures were not collected if they did so). Identical measures were completed at each time point, with the exception of demographics, which were collected only at baseline. At every assessment, participants were given a fifteen-dollar gift card for completing the online questionnaires and an additional five dollars for every day that they completed the online sleep diary, for a potential total of fifty dollars.

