### Measures

**Demographics.** Demographic information included age, date of birth, ethnicity, sex, height, weight, and concussion history.

**Insomnia Severity Index (ISI).** The ISI is widely used to measure insomnia severity and treatment response in sleep research. The ISI is a seven-item self-report questionnaire that assesses sleep onset latency, sleep efficiency, and functional impact from sleep issues. The sleep latency and efficiency items are rated on a 5-point Likert scale from 0 (*none*) to 4 (*very severe*). The remaining four items measure dissatisfaction, how noticeable sleep problems are to others, distress from sleep problems, and interference with daily functioning (all rated on 5-point Likert scales). Total scores on the ISI range from 0-28. Although the ISI was originally designed for adults, it has been shown to be valid in adolescent populations. In a clinical sample, an ISI score  $\geq 11$  has been shown to have 97% specificity and 100% specificity to detect insomnia. The current study used a cut score of  $\geq 12$  for eligibility to maximize the likelihood that participants had clinically significant insomnia symptoms. The ISI total score was the primary outcome measure for treatment response.

**Pittsburgh Sleep Quality Index (PSQI).** The PSQI is a widely used brief self-report measure of sleep quality aimed at examining the facets of sleep disturbance . It is composed of 19 items that measure sleep disruptions in the month prior to questionnaire completion. The PSQI contains seven subscales: subjective sleep quality, sleep latency, sleep duration, habitual sleep efficiency, sleep disturbances, use of sleep medications, and daytime dysfunction, which are combined into a total sleep quality score. The total PSQI raw score ranges from 0 to 21, with higher scores representing worse sleep disturbance; scores of greater than 5 indicate clinically significant sleep disruption . PSQI scores have adequate internal consistency . Additionally, the PSQI has shown validity for assessing sleep disturbances in adolescents following traumatic brain injury .

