### Statistical Analysis

All analyses were conducted using SPSS 25.0^22. Baseline demographic and medical variables for the two conditions were compared using one-way ANOVAs and  $\chi^2$  tests. Intent-to-treat (ITT) analyses were conducted in line with CONSORT guidelines (i.e., all participants who

started the intervention were included) . ITT analyses were completed using maximum likelihood linear mixed model analyses. Between-group differences on primary and secondary outcome variables were also analyzed using linear mixed models. Linear mixed models are considered robust with respect to inclusion of participants with missing data in repeated measures research and are considered superior to traditional repeated measures ANOVA for longitudinal designs . Treatment group (CBT-I or TAU) was specified as the between-subjects factor, and time of measurement was the within-subjects factor. The effect of interest was the treatment group by time interaction coefficient. Models were tested to include a linear and quadratic time coefficient; in final models the quadratic time coefficient was removed for all analyses in which it was not significant. Multiple structures were tested for sigma, and the identity structure was chosen because it provided the best Schwarz's Bayesian Information Criterion (BIC) for each model. The treatment group variable was introduced as a dummy-coded variable with TAU as reference group. An  $\alpha$  of 0.05 was used to determine statistical significance. Effect sizes of 0.20, 0.50, and 0.80 were interpreted as indicating small, medium, and large effects, respectively. Standardized effect sizes for linear mixed models were derived by calculating standard deviation (SD)pooled =  $\sqrt{\frac{((\text{standard error } [se]_1 \cdot \sqrt{n_1})^2 \cdot (n_1 - 1) + (se_2 \cdot \sqrt{n_2})^2 \cdot (n_2 - 1))}{(n_1 + n_2 - 2)}}$  based on existing recommendations .

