Other sleep data outcomes included change in PSQI, DBAS, and sleep diary measures. Most participants provided at least some sleep diary data. On average, participants provided data for 5.6 / 7 days at each assessment. Specifically, sleep diaries were completed by all 24 participants at baseline (mean days of completion = 6.0), by 19 participants at post-treatment (mean days of completion = 5.0), and by 20 participants at the four-week follow-up (mean days of completion = 5.7). All available sleep diary data were included in analyses.

Clinically significant change in ISI scores—the primary outcome variable—was also assessed in two ways. First, a variable indicating whether the ISI changed eight points or more was tested—a change of this magnitude is accepted as a meaningful change in CBT-I trials . Additionally, we calculated and analyzed the proportion of participants in each condition that reached a score below a cut-off of 8 (i.e., 0-7) on the ISI at each time point, indicative of “absence of insomnia” . To compare the proportion of participants who exhibited clinically significant change or reached a score below the cut-off, Fisher’s exact tests were used.

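### Allocation was blocked by gender but the outcome mixed models leave gender out, so the group-by-time test is mildly conservative if gender predicts change

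*Combined protocol and SAP*

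**What the plan says.** Under Trial Design, allocation to CBT-I or TAU was made "using a gender blocked computer-based randomization tool". Gender is the only balancing factor named, and no block size is given. Participants and Procedures reports 24 adolescents randomised, 12 to each arm, but not how many of each gender.

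The Statistical Analysis section defines the outcome models thus: "Treatment group (CBT-I or TAU) was specified as the between-subjects factor, and time of measurement was the within-subjects factor". It adds: "The effect of interest was the treatment group by time interaction coefficient". No covariate or stratum is mentioned for any mixed model. The responder comparisons use Fisher's exact tests, with no stratification described. The plan gives no reason for leaving the blocking factor out and no sensitivity analysis that includes it.

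The one place where a related variable could enter is the baseline comparison ("Baseline demographic and medical variables for the two conditions were compared using one-way ANOVAs and" chi-square tests), because sex is among the demographic items. That table describes the two arms; it is not part of the treatment comparison.

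**The concern.** Blocking on a factor makes the arms more alike on it than chance would. The treatment estimate then varies less from one possible randomisation to another. A model without the factor does not recognise this: it counts the differences between genders as unexplained error and reports a standard error that is too large whenever gender is related to the response. The test then rejects too rarely under no effect and loses some power. With 12 per arm there is little precision to spare, and the information needed to recover it is already held.

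Because the effect of interest is group by time, what matters is whether gender predicts change over the three assessments, not whether it predicts the level of the ISI or the other scales.

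**Working it through.** The plan contains no power or sample-size figure, so there is nothing of its own to reproduce. The check asks what omitting gender does to the group-by-time test.

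**Inputs from the documents:** 12 per arm; three assessments (baseline, post-treatment, four-week follow-up); alpha 0.05; group by time as the effect of interest.

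**Assumed, because the documents do not say:** two-sided test; random intercept; within-subject correlation 0.5; outcome SD of 1 within gender; equally spaced visits with linear change; 16 of one gender and 8 of the other, split evenly between arms; complete data; gender acting linearly on change; true slope difference 0.5 SD per visit.

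**Step 1. Correct standard error.** The within-person residual variance is 1 − 0.5 = 0.5. With visits coded −1, 0, 1, a participant's slope is (third value − first value)/2, with variance 0.5/2 = 0.25. A gender effect that is constant over time cancels here. The standard error of the slope difference is √[0.25 × (1/12 + 1/12)] = 0.204.

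**Step 2. Size of the gender effect.** Let gender shift the slope by γ per visit, and let p = 16/24, so p(1 − p) = 2/9. Change from first to third visit has within-gender variance 2 × 0.5 = 1. Gender's share of the variance in change is 4γ²(2/9) / [4γ²(2/9) + 1].
- Share 10%: 4γ²(2/9) = 1/9, so γ² = 0.125.
- Share 20%: 4γ²(2/9) = 0.25, so γ² = 0.281.

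**Step 3. Standard error when gender is omitted.** The gender variation adds 2 × 24 × (2/9) × γ² = 10.67γ² to the residual sum of squares. The within-person degrees of freedom are 72 − 24 − 2 = 46.
- Share 10%: residual variance (46 × 0.5 + 1.33)/46 = 0.529; reported standard error √(0.529/12) = 0.210.
- Share 20%: (46 × 0.5 + 3.00)/46 = 0.565; reported standard error √(0.565/12) = 0.217.

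Because the arms are balanced on gender, the true standard error stays at 0.204.

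**Step 4. Error rate and power.** The critical t on 46 degrees of freedom is 2.013. Judged against the true standard error, the effective threshold is 2.013 × 0.210/0.204 = 2.07 at 10%, and 2.013 × 0.217/0.204 = 2.14 at 20%. The two-sided tail areas are 4.4% and 3.8%. Power is roughly Φ(0.5/0.204 − threshold), where 0.5/0.204 = 2.45: Φ(0.38) = 65% and Φ(0.31) = 62%. With gender-by-time in the model the threshold is about 2.01, and power is Φ(0.44) = 67%.

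**Step 5. Simulation, 40,000 trials per case.**

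| Gender's share of variance in change | Type I error without gender | Power without | Power with gender-by-time |
|---|---|---|---|
| 0% | 5.0% | 67% | 67% |
| 10% | 4.3% | 65% | 67% |
| 20% | 3.6% | 62% | 67% |

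The closed form agrees to within 0.2 percentage points on type I error and to the nearest point on power.

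**The case against.** The strongest reply is that nothing here threatens validity. The allocation leaves the estimate unbiased, type I error stays at or below 5%, and this is a pilot. No part of the documents says that gender predicts change on any scale, so the shares of 10% and 20% are assumptions and the loss may be nil. All of that stands, and it limits how much weight the point can bear.

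It is also true that exact balance within gender is assumed. Without block size or gender counts it cannot be confirmed. Nor need it survive missing data: sleep diaries came from 24 participants at baseline, 19 at post-treatment and 20 at follow-up. The figures above are therefore indicative.

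Three stronger readings are tempting, and the documents do not support them.

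- *A larger loss.* Regressing a single change score on treatment, with and without gender, gives a power difference of about 4 points at a 10% share and 8 to 9 at 20%. That is not the planned analysis. In a three-visit model with a random intercept the difference is about half as large, and a constant gender effect cancels.
- *A large gain from a gender main effect.* The plan reports that "the identity structure was chosen because it provided the best Schwarz's Bayesian Information Criterion (BIC) for each model" and does not say whether a random intercept was fitted. With identity residuals and no random intercept, adding a gender main effect raises simulated power from 37% to 43% (gender explaining 10% of outcome variance) or from 35% to 49% (20%). But that model's type I error is already below 1%, because within-person correlation is ignored. That is a separate question which the text leaves open; these gains should not be credited to the blocking factor.
- *A mismatch between sex and gender.* The demographics item reads: "Demographic information included age, date of birth, ethnicity, sex, height, weight, and concussion history". A reader might infer that the blocking variable differs from the recorded one. Each word is used once in this connection, and nothing shows that two variables were held or that any participant was classified differently. Interchangeable use is at least as likely.

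**Conclusion.** The point holds, at modest size. The factor used to restrict randomisation is absent from the outcome mixed models, and no reason is given. The consequence is a mildly conservative group-by-time test if gender predicts change: about 2 points of power at a 10% share of the variance in change and about 5 points at 20%, with nothing lost at 0%. It is not bias and not an excess of false positives.

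These sizes rest on the assumptions listed in the working, chiefly a random intercept, balance of gender across arms and complete data. The gap is minor but worth closing, because including the factor costs nothing measurable in power when gender is irrelevant.

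**What to change.** Add the blocking factor, with values taken from the randomisation list, and its interaction with time as fixed effects in the mixed models. Keep group by time as the effect of interest. State the block size and the number of each gender in each arm, so that the balance can be judged.

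The document describes the analyses as already carried out, so this should not silently replace the reported model. Present the adjusted result beside it, so that both are visible and no choice between them appears to depend on the results. If the factor is to stay out, say why.

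The cost is refitting the models, with one or two degrees of freedom spent in each. No new data are needed.

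### Gender was used to block randomisation but is left out of the mixed model, and time since injury, open from 1 to 12 months, is used in neither.

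*Combined protocol and SAP*

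**What the plan says.** Under Trial Design, participants were allocated "using a gender blocked computer-based randomization tool". No other stratification factor is named and no block size is given. Participants and Procedures reports 24 adolescents randomised, 12 to each arm.

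Under Statistical Analysis, "Treatment group (CBT-I or TAU) was specified as the between-subjects factor, and time of measurement was the within-subjects factor". Time is linear, with a quadratic term kept where significant. No covariate is named. The target is stated as follows: "The effect of interest was the treatment group by time interaction coefficient". On covariance, "Multiple structures were tested for sigma, and the identity structure was chosen"; random effects are not described. Baseline demographic and medical variables are compared between arms, but no adjustment is tied to the result.

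Inclusion criterion 3 requires "being at least 1 month but no more than 12 months post-injury to ensure symptoms were no longer acute, yet current and persistent". On the source of the sample, "Adolescents were referred to the ACH Brain Injury Clinic based on persistent post-concussion symptoms". The post-treatment assessment comes at seven weeks and the follow-up about four weeks after treatment, so each participant is observed for roughly 11 weeks.

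**The concern.** Two omissions bear on the primary contrast.

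**Gender.** Blocking on a factor tends to balance it between arms, which removes its contribution from the true variability of the arm difference. A model that ignores the factor still counts that contribution as residual noise. The reported standard error is then larger than the real one, and a small trial gives away power.

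**Time since injury.** The contrast is a difference in change, so a variable that predicts rate of change acts on it directly. Someone entering at 1 month is observed over roughly months 1 to 4, and someone entering at 12 months over roughly months 12 to 15. If expected recovery differs across that window, a chance imbalance goes unadjusted into the group-by-time coefficient. The same reasoning applies to the HBI, which measures post-concussive symptoms themselves, although no calculation has been made for it. Criterion 3 shows that the investigators thought time since injury relevant to who should enter, and it is not used again.

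**Working it through.** The documents give no sample-size calculation, SD or target effect, so there is no planned figure to reproduce. The inputs from the documents are 12 per arm, alpha 0.05 (taken as two-sided; sidedness is not stated) and the 1-12 month window. The rest are assumptions.

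**Gender**

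Assumptions: one change score per participant, SD of ISI change within gender 5, and six of each gender in each arm.

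- True SE of the arm difference = 5 × √(1/12 + 1/12) = 5 × 0.408 = 2.04. Gender is balanced, so a gender difference D in change cancels and this value does not depend on D.
- Variance the model estimates when gender is omitted: s² = 25 + (D²/4) × (24/22). For D = 4 this is 25 + 4 × 1.091 = 29.36, so the reported SE is 5.42 × 0.408 = 2.21.
- The effect giving 80% power on a t test with 22 df is 1.197 SD, or 1.197 × 5 = 5.98 points.

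| Gender difference in change, D | True SE | Reported SE | Type I error | Power |
|---|---|---|---|---|
| 0 | 2.04 | 2.04 | 5% | 80% |
| 2 | 2.04 | 2.09 | 4.4% | 79% |
| 4 | 2.04 | 2.21 | 3.7% | 75% |
| 6 | 2.04 | 2.41 | 2.3% | 69% |

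Type I error and power come from simulation. A repeat with 200,000 simulated trials gave type I errors of 4.5%, 3.5% and 2.2% and the same rounded powers, so the differences are simulation error. With gender in the model, type I error was 4.9-5.0% and power 80% at every D. If gender is irrelevant, the price is 21 df instead of 22, which takes power at 5.98 points from 80.0% to 79.8%.

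**Time since injury: how often the arms differ**

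Assumption: entry times uniform on 1-12 months.

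- SD = 11/√12 = 3.18 months.
- SE of the difference in arm means = 3.18 × 0.408 = 1.30 months.
- P(difference ≥ 2 months) = 2 × [1 − Φ(2/1.30)] = 12%. For 1 month or more it is 44%.
- If the SD were 2 or 4 months instead, the 2-month figure would be 1.4% or 22%.

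**Time since injury: what an imbalance could do**

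Suppose 6 to 12 of the 24 improve by an extra 4 ISI points (assumption). From the hypergeometric split over 12:12, the SD of the resulting difference between arms is 0.72 to 0.83 points, a 95% range of about ±1.4 to ±1.6.

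A separate simulation under no treatment effect used three equally spaced visits, between-subject SD 3, residual SD 2.5 and a linear recovery gradient across the window. At a 4-point gradient, a random-intercept model had a type I error of 5.6% overall and about 10% in allocations with an imbalance of 2 months or more. A test on subject-specific slopes held 4.7-5.2% overall across gradients of 0 to 8 points.

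**Time since injury: what adjustment buys**

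Residual SD of change 5, 12 per arm, uniform entry times, continuous months since injury in the model. The recovery difference was taken either as an extra improvement in the earliest 18%, 30% or 45%, or as a linear gradient across the window.

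| Difference in recovery (ISI points) | Change in SD of the effect estimate |
|---|---|
| 0-2 | 1-3% larger |
| 4 | roughly none to 3% smaller |
| 6 | 2-9% smaller |

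**The case against.** The strongest defence is that this is a pilot of 24 with a deliberately simple model, and a second stratum would have left thin cells. That stands as a defence of not stratifying on time since injury. It does not explain leaving out the factor that was blocked on.

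A reader might infer that the sample mixes adolescents still recovering with others at a plateau. The documents do not support this. They give neither a recovery curve nor a distribution of time since injury, and the referral route and criterion 3 both aim at persistent symptoms. Different expected recovery is a possibility only.

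A reader might also infer that the treatment effect is biased. It is not, on average: randomisation makes any imbalance a matter of chance, and a standard error that reflects variation between participants' slopes already covers it. The inflation seen with random intercepts only is a question of random-effects specification, which the documents leave open.

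Finally, a reader might expect adjustment to gain 2-4% in precision at 4 points and 7-12% at 6. Gains of that size need the true early/late indicator, which no analyst would have. Continuous months gain less.

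One caution applies to the gender figures. They hold for an analysis in which each participant contributes one change. If the identity structure means fully independent residuals, the interaction test was already very conservative in simulation (type I error under 1%), whatever is done about gender.

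**Conclusion.** The gender point stands as a mismatch between randomisation and model. Its direction is loss of power, not false positives: negligible at a 2-point gender difference in ISI change, about 5 percentage points of power at 4, and about 11 at 6. These sizes rest on an assumed SD of 5, equal gender numbers and effective balance within arms. The documents report neither the gender split nor any gender effect.

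The time-since-injury point stands in a weaker form. The variable is unused, and an imbalance of 2 months or more is plausible (about 12% under uniform entry). Readers of the one allocation that occurred need to see whether it happened. The documents do not show that it distorted the result, and the expected precision gain does not justify putting the term in the primary model.

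**What to change.** 1. Add gender and gender-by-time to the mixed models, with gender-by-quadratic-time wherever the quadratic is kept. The interaction is the term that matters; a main effect alone leaves the group-by-time coefficient almost unchanged. Use the variable actually used for blocking, because Trial Design says gender while the Demographics entry records sex. The cost is two fixed effects (more with quadratic time) and almost no power if gender is irrelevant. The reason for the change is the randomisation, not the data, but the document postdates recruitment, so show the group-and-time result beside it.
2. Report time since injury by arm. Eligibility already required it, so no new data are needed.
3. Add one sensitivity model each for the ISI and HBI, with continuous months since injury and its interaction with time. Run it whatever the baseline tests show. Label it post hoc: the document is dated September 2018 and recruitment ended in August 2017. The cost is two further fixed effects with 24 participants, and an estimate 1-3% less precise if recovery hardly varies across the window.
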